5.2.3 Rituximab Adjuvant Therapy

Starting at 12 months, after collection of the 12-month PCR samples (Sec 7.2), rituximab will be given monthly for 6 doses total.

The dose will be 375 mg/m^2 IV. Interferon maintenance will usually have commenced about 3-4 months before the rituximab doses start. When IFN and rituximab doses are given in the same month, the rituximab dose will be given first, with decadron permitted (but not mandatory) and the IFN will begin on day 2 of each cycle, or may be delayed for 1-2 days if needed (see 5.7.3).

When rituximab is given by itself (without IFN), decadron 8 mg IV or PO as a pre-medication is permitted but not mandatory (and see also 5.4).

5.3 ARM 2 (concurrent anti-CD20 arm) will consist of FND in conjunction with rituximab. Rituximab will be given on days 1 and 8 of course 1, then on day 1 only of courses 2-5, as outlined below:

- course 1:

rituximab 375 mg/m^2 d.1 & 8 IV  
(see section 5.4 for details of administration)  
fludarabine 25 mg/m^2 d. 2-4 IV  
mitoxantrone 10 mg/m^2 d.2 IV  
dexamethasone 20 mg d. 1-5 IV or PO  
(note dexamethasone starts a day earlier than in the usual FND schedule, so that the first dose of rituximab is given in conjunction with steroid)

- courses 2-5:

rituximab 375 mg/m^2 d.1 IV  
(see section 5.4 for details of administration)  
fludarabine 25 mg/m^2 d. 2-4 IV  
mitoxantrone 10 mg/m^2 d.2 IV  
dexamethasone 20 mg d. 1-5 IV or PO  
(note dexamethasone starts a day earlier than in the usual FND schedule, so that the first dose of rituximab is given in conjunction with steroid)

- courses 6 - 8:

same as for arm 1 (i.e., FND without concurrent rituximab) -- see Section 5.2, especially 5.2.1 and 5.2.2 concerning interval (q28 d), guidelines for use of G-CSF (applicable for all courses), and guidelines for omitting courses 7 & 8 if there is cumulative myelosuppression

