## 7.0 EVALUATION DURING STUDY (SEE APPENDIX A)

- 7.1. Patients shall be followed at least weekly with CBC, platelet count and differential and will be seen in our clinic after the second and fourth courses.
- 7.2 PCR in the peripheral blood will be followed every 6 months during the first 3 years, then every 12 months. PCR in the bone marrow will be followed every 6 months during the first 3 years, and every 12 months subsequently. For patients who are positive at the 6 month time point an additional PCR assay at 9 months is requested. For such patients who are still positive at 9 months, but who are subsequently negative at 12 months, yet another additional assay at 15 months is requested.
- 7.3 An SMA-12 shall be performed at least every other course or as frequently as needed to define drug toxicity.
- 7.4 Peripheral blood lymphocyte surface markers and Ig's every 3 months during therapy, and at least every 6-12 months off therapy until any abnormalities resolve.
- 7.5. Appropriate restaging every 3 courses, to include at least CXR, CT abdomen and pelvis, and BM Bx, and other tests to assess baseline measurable and assessable disease sites.
- 7.6 Cardiac re-evaluation as clinically indicated.
- 7.7 Off therapy monitoring should include restaging assessments (as outlined in section 7.5) at least every 6 months until relapse, or through year 5, and at least yearly thereafter.

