## 8.2 Response Definitions:

- I. A molecular complete remission is defined as a patient with an initially positive peripheral blood PCR who converts to negative on at least 2 consecutive occasions no less than 2 months apart. If, during the interval when 2 consecutive blood PCR's are negative, a marrow PCR is positive, such patients would not be considered a molecular complete responder. (Such cases of discordance are infrequent but can occur).
- II. Clinical CR: defined as those who achieve a normal state which includes no detectable evidence of disease on x-rays.
- III. Clinical CRu: defined as "CR unconfirmed" on the basis of minimal residual abnormalities on x-ray such as a residual mass <25% of original measurement (either by volume calculation or by the product of 2 diameters -- See Sect. 8.1) with no palpable disease on physical examination.
- IV. Clinical PR: a) 50-75% reduction in the product of palpable tumor diameters of in the tumor volume measurements by radiologic criteria (See Sect. 8.1) or any palpable disease such as peripheral node(s) > 1 cm in diameter or palpable abdominal mass with histological evidence of lymphoma cells.
- V. Clinical minor response or failure includes, <50% tumor shrinkage or > 50%, but with tumor regrowth between courses.

- 8.3 All toxicities encountered during the study will be evaluated according to the grading system (0-4) in Appendix D and recorded prior to each course of therapy. Duration and treatment will be recorded. Life-threatening toxicities should be reported immediately to the Study Chairman.

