## 10.0 STATISTICAL CONSIDERATIONS

### 10.1 Design:

The study will consist of a randomized controlled trial comparing two schedules of the anti-CD20 antibody rituximab, integrated with an established effective front-line chemotherapy program, FND. The primary endpoint will be the molecular complete response rate 12 months after the start of treatment. Since molecular response requires 2 consecutive negative PCR's (see 8.2, part I), a 12-month negative PCR will be considered truly negative only if a 9 or 15 month (or both) are also negative.

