### 10.3 Adequacy of Sample Size:

Preliminary experience with the intensive regimen (CHOD-B/ESHAP/NOPP) has shown that a molecular CR rate in the neighborhood of 60-65% can be expected. Preliminary evidence indicates that a similar fraction of patients achieve molecular CR with FND.

An additional impact of rituximab is anticipated, since rituximab, when used singly, is capable of achieving blood and marrow molecular response, and rituximab has been integrated with CHOP chemotherapy with attainment of more molecular responses than would be expected with CHOP alone. Both the rapidity of attaining PCR-negative status, and the durability of the PCR-negative state, are additional molecular endpoints of interest. Thus, we intend to address if:

- a. the addition of biotherapy with chimeric anti-CD20 antibody to FND chemotherapy can induce a higher molecular response rate at 12 months than FND alone. This is the primary endpoint of this trial. The delayed administration of anti-CD20 given after 12 months, as in arm #1, will allow us to investigate this point. Sixty-four PCR-positive patients would be required in each arm to detect a difference of 25% in the 12-month molecular CR rates, assuming that the higher response rate was 85%. This assumes a two-sided  $\alpha$  level of 0.05 and a power of 0.90.
- b. the addition of biotherapy with anti-CD20 to FND chemotherapy (arm #2) is capable of inducing a higher molecular response rate at 6 months, as well as the 12 month primary endpoint, when compared with FND chemotherapy alone (arm #1).

c. the addition of delayed anti-CD20 biotherapy after 12 months will then raise the molecular response rate at 18 months as compared with 12 months in the same patient. We will also compare the molecular response at 18 months with patients randomized to arm #2 (concurrent therapy) at the same timepoint.

d. either of the two arms is associated with a more prolonged or sustained molecular response (as measured at 2 years from initiation of chemotherapy).

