APPENDIX A  
 ACTIVITY FLOW CHART

	PRE STUDY	WEEKLY	EVERY 2 COURSES	EVERY 3 COURSES	EVERY 6 MONTHS	POST-THERAPY
H & P	X		X			q 3-6 mo
PS	X					
CBC	X	X				q 3-6 mo
U/A	X					
CXR	X					q 3-6 mo ‡
SMA 12, K, MG*	X		X			q 3-6 mo
B2M	X			X		q 3-6 mo
BX/FNA*	X					
BM BX	X			X		q 6 mo ‡
LAG, CTs	X			X		q 6 mo ‡
PB markers, Ig's	X			X***		
PB PCR	X				X**	
BM PCR	X				X**	
ECHO or MUGA	X					

♣ K, Mg, etc as indicated, mainly for pts on ATT (see App. B)

\* when accessible; for phenotype, gene rearrangement

\*\* PCR for bcl-2 q 6 mo yr 1-3, q 12 mo thereafter. Contingency for PCR monitoring at 9 and/or 15 months for selected patients (see 7.2)

\*\*\* PB markers, Ig's: until recovery to normal

‡ Restaging off therapy (see section 7.7): at least q 6 mo until relapse or through year 5; then at least yearly.

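### Section 10.1 confirms a 12-month negative PCR only by a 9- or 15-month negative, but 7.2 schedules neither for patients negative at 6 and 12 months, whom 8.2 counts as molecular complete responders

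*Combined protocol and SAP*

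**What the plan says.** The primary endpoint (10.1) is the molecular complete response rate 12 months after treatment starts. Section 10.1 invokes the two-consecutive-negatives requirement of 8.2 and then sets its own rule: "a 12-month negative PCR will be considered truly negative only if a 9 or 15 month (or both) are also negative".

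Section 8.2, part I, defines a responder as an initially blood-PCR-positive patient "who converts to negative on at least 2 consecutive occasions no less than 2 months apart", unless a marrow PCR is positive in that interval.

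Section 7.2 sets blood PCR every 6 months for the first 3 years and adds two conditional assays. The first: "For patients who are positive at the 6 month time point an additional PCR assay at 9 months is requested". The second covers those in that group "who are still positive at 9 months, but who are subsequently negative at 12 months, yet another additional assay at 15 months is requested". The PCR footnote to the flow charts (abstract and Appendix A) describes these as a "Contingency for PCR monitoring at 9 and/or 15 months for selected patients (see 7.2").

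On rituximab timing, 5.2.3 says for arm 1: "Starting at 12 months, after collection of the 12-month PCR samples (Sec 7.2), rituximab will be given monthly for 6 doses total". Section 5.3 says for arm 2: "Rituximab will be given on days 1 and 8 of course 1, then on day 1 only of courses 2-5".

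Section 10.3.b asks whether concurrent rituximab "is capable of inducing a higher molecular response rate at 6 months, as well as the 12 month primary endpoint".

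**The concern.** The rule that decides the primary endpoint asks for a sample that the visit schedule does not request from one group of patients: those already negative at 6 months. Sections 8.2 and 10.1 then give different answers for the same patient. The affected patients are the fastest converters, and the trial hopes to see more of them in arm 2. If the rule were applied as written, responders would be lost from the numerator, probably more of them in arm 2. If it were settled later instead, the scoring of the primary endpoint would be decided after data exist.

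**Working it through.** **Plan's own figure.** Section 10.3.a gives 64 PCR-positive patients per arm for 85% vs 60%, two-sided alpha 0.05, power 0.90. The usual two-proportion formula without continuity correction gives 65, and the arcsine formula gives 63.8, i.e. 64. Exact power of the two-sided pooled z-test at 64 per arm is 0.903. The sample size is not in question.

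**Tracing each path.** For a patient negative at 12 months who is sampled as 7.2 requests:

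| 6 months | 9 months | 15 months | 8.2 | 10.1 as written |
|---|---|---|---|---|
| negative | not requested | not requested | met (6 and 12) | cannot be confirmed |
| positive | negative | not requested | met (9 and 12) | confirmed at 9 |
| positive | positive | requested | met if 15 is negative | confirmed only at 15 |

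The first row is the contradiction. It needs no numerical assumption.

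**Size, by assumption.** Let e be the share of 12-month molecular responders already negative at 6 months. The documents give no value for it. Nor does 10.1 say how an unconfirmed patient is scored, so both options are shown. With p = 60% or 85%:

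- scored as non-responder: observed rate = p(1 − e), 64 per arm;
- dropped as inevaluable: observed rate = p(1 − e)/(1 − pe), with 64(1 − pe) patients left, rounded.

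| e, arm 1 / arm 2 | Non-responder: rates | Power | Dropped: rates | Power |
|---|---|---|---|---|
| 10% / 10% | 54.0% vs 76.5% | 0.777 | 57.4% vs 83.6% | 0.895 |
| 25% / 25% | 45.0% vs 63.75% | 0.563 | 52.9% vs 81.0% | 0.877 |
| 50% / 50% | 30.0% vs 42.5% | 0.323 | 42.9% vs 73.9% | 0.821 |
| 30% / 50% | 42.0% vs 42.5% | 0.052 | 51.2% vs 73.9% | 0.59 |

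For the last row: 0.60 × 0.70 = 0.420 and 0.85 × 0.50 = 0.425. Dropped, 0.420/(1 − 0.18) = 0.512 and 0.425/(1 − 0.425) = 0.739.

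**Late converters (third row of the path table).** Their only scheduled confirmation is at 15 months. In arm 1, monthly dosing from month 12 puts doses at months 12, 13 and 14 before that sample: three, or four if monthly means every 28 days. In arm 2 the last dose is on day 1 of course 5, about 4 × 28 = 112 days after the start if courses run on time. Rituximab could therefore keep negative an arm 1 late converter who would otherwise have reverted.

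Arm 1 inflation = q × r × s, where q is the share of arm 1 who are late converters, r the share of these who would revert without rituximab, and s the share of reversions suppressed. None of the three is in the documents. Assumed ranges are q 5–20%, r 10–50% and s 50–68%; the s range borrows the single-agent conversion rates in 2.4, which measure something different.

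- Low end: 0.05 × 0.10 × 0.50 = 0.25 points, power 0.898.
- High end: 0.20 × 0.50 × 0.68 = 6.8 points, power 0.685.
- Over q of 5, 10, 15, 20%, r of 10, 25, 50% and s of 50, 68%, power stays at or above 0.80 in 21 of 24 combinations. The other three need r = 50% with q of 15–20%.
- With both true rates at 60%, two-sided rejection is 0.054 without inflation and 0.131 at the high end, of which 0.128 favours arm 1.

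**The case against.** The best reply is that the intent is plain. Section 10.1 presents its rule as an application of 8.2, and 8.2 accepts negatives at 6 and 12 months. The 7.2 contingencies fit: extra assays are requested only where the 6- and 12-month pair cannot confirm, so a patient negative at 6 months plausibly has no 9-month assay because none is needed. This is persuasive as to intent, and it makes the problem a wording gap, not a design failure. It does not remove the gap: the written condition is exclusive, and no text covers these patients.

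A reader might infer from the table that the trial loses most of its power, or that its difference disappears. The documents do not support that. Those figures need a literal reading that was probably not meant, values of e that the plan does not give, and scoring as non-response, which 10.1 does not state. Section 10.2 allows for inevaluable cases, and if these patients are dropped, equal shares cost much less. Harm remains under either scoring when arm 2 converts faster.

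A reader might also infer that the arm 1 rituximab doses undermine the comparison with FND alone. That goes too far. The 12-month sample is drawn before the first arm 1 dose, so rituximab cannot turn a 12-month positive into a responder. If arm 2 is better, the effect shrinks the difference; it cannot produce a false win for arm 2. If the arms are equal, it favours arm 1.

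**Conclusion.** Sections 10.1, 7.2 and 8.2 disagree about patients negative at 6 and 12 months. Read literally, 10.1 cannot count the earliest responders, and the loss would tend to fall harder on arm 2. That conclusion rests on the text alone.

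The size cannot be derived from the documents. The power figures illustrate assumed shares under two possible scorings and are not forecasts. The gap concerns the primary endpoint and closes with one clause, so it should be closed.

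The 15-month sample in arm 1 is a secondary matter of reporting. Its effect ranges from negligible to moderate on unsourced assumptions, and it is conservative if arm 2 is truly better.

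**What to change.** **Reword 10.1.** A 12-month negative PCR is confirmed by a negative at the immediately preceding PCR (the 9-month if done, otherwise the 6-month) or by a negative at 15 months. The marrow rule in 8.2 is unchanged.

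**Cover the remaining gap.** The 9-month assay is only requested, so some patients positive at 6 months may lack it and be negative at 12; 7.2 then triggers no 15-month assay. State that a negative 15-month PCR, if drawn, confirms such a patient, and that otherwise the response is unconfirmed. State also whether unconfirmed patients count as non-responders or as inevaluable.

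**Reporting note.** Give the number of 15-month-only confirmations in each arm, and say that in arm 1 those samples followed about three rituximab doses.

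An analysis restricted to responses confirmed by month 12 is optional and should be descriptive only, because it favours the faster-converting arm. Take true rates of 60% in both arms, late converters of 15% vs 5%, and r = 50%. It then removes 15% × 50% = 7.5 points from arm 1 and 5% × 50% = 2.5 from arm 2, and so compares 52.5% with 57.5%. Two-sided rejection is 0.086, of which 0.080 favours arm 2. With 15% late converters and r = 50% in arm 1, the existing 15-month route gives 0.077 to 0.097 (s of 50% to 68%), mostly favouring arm 1. One bias would replace another of similar size.

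**Cost.** A few sentences and one count per arm, with no new samples and no change to 7.2 or to treatment. The price is that a patient negative at 6 and 12 months is accepted without an intermediate sample, which 8.2 already allows.

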### 10.2 Accrual Rate:

The average yearly accrual rate during the past 4 years on the current low grade lymphoma stage IV clinical trial has been 33 patients per year. Previous experience at M.D. Anderson Hospital has shown that the PCR positivity rate in these stages is in the neighborhood of 60% when tested with the mbr probe only. If the mcr probe is added, approximately 75% of patients can be expected to have a positive PCR at the time of diagnosis. Accrual of the target 128 evaluable patient (see 10.3 e) will therefore take just over 5 years (estimated 5 years, 2 months). Allowing for some inevaluable cases (9% on protocol 88-050), a total accrual of about 185 patients is planned. [Amendment May 2001: Planned accrual changed to 210 patients, with restriction of eligibility to follicular lymphoma only for the last 25-30 patients, so that adequate numbers are entered to fulfill the goal outlined in 10.3.a below. This amendment results from higher-than-expected numbers of patients with small lymphocytic (including MALT) lymphoma being entered.]

### 10.3 Adequacy of Sample Size:

Preliminary experience with the intensive regimen (CHOD-B/ESHAP/NOPP) has shown that a molecular CR rate in the neighborhood of 60-65% can be expected. Preliminary evidence indicates that a similar fraction of patients achieve molecular CR with FND.

An additional impact of rituximab is anticipated, since rituximab, when used singly, is capable of achieving blood and marrow molecular response, and rituximab has been integrated with CHOP chemotherapy with attainment of more molecular responses than would be expected with CHOP alone. Both the rapidity of attaining PCR-negative status, and the durability of the PCR-negative state, are additional molecular endpoints of interest. Thus, we intend to address if:

- a. the addition of biotherapy with chimeric anti-CD20 antibody to FND chemotherapy can induce a higher molecular response rate at 12 months than FND alone. This is the primary endpoint of this trial. The delayed administration of anti-CD20 given after 12 months, as in arm #1, will allow us to investigate this point. Sixty-four PCR-positive patients would be required in each arm to detect a difference of 25% in the 12-month molecular CR rates, assuming that the higher response rate was 85%. This assumes a two-sided  $\alpha$  level of 0.05 and a power of 0.90.
- b. the addition of biotherapy with anti-CD20 to FND chemotherapy (arm #2) is capable of inducing a higher molecular response rate at 6 months, as well as the 12 month primary endpoint, when compared with FND chemotherapy alone (arm #1).

c. the addition of delayed anti-CD20 biotherapy after 12 months will then raise the molecular response rate at 18 months as compared with 12 months in the same patient. We will also compare the molecular response at 18 months with patients randomized to arm #2 (concurrent therapy) at the same timepoint.

d. either of the two arms is associated with a more prolonged or sustained molecular response (as measured at 2 years from initiation of chemotherapy).

e. the FFS of patients in the concurrent arm is different from the delayed arm. This is the secondary efficacy endpoint for which we can expect information on a reasonable time frame. (For survival, long-term follow-up is intended, but mature data requires 5-10 years follow-up -- which serves to emphasize the need to identify reliable surrogate endpoints). A 3-year FFS of 50% with standard therapy is typical. Assuming one FND plus rituximab scheme matches this standard expectation, and the other exceeds it by 20%, the trial will have power of 0.66 to detect a difference of this size at significance level of 0.05. This assumes that 128 patients will be entered at the rate of two patients per month, that FFS is distributed exponentially, and that all patients will be followed for a minimum of one year. Nonetheless, this data will: (a) be an important endpoint to correlate with the molecular remission data; and (b) hopefully provide hypothesis-generating information for future, larger-scale trials.

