**STATISTICAL CONSIDERATIONS:**

The average yearly accrual rate for the current stage IV trial has been 33 patients per year. About 75% of patients can be expected to have a positive PCR. It will take 64 PCR positive patients in each arm to detect a difference of 25% in the twelve month molecular CR rate, assuming that the higher response rate was 85%. This assumes a two-sided alpha level of 0.05 and a power of 0.90.

Allowing for some inevaluable cases, approximately 210 patients will be accrued, which will probably take a little over 5 years.

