5.7.2 Maintenance (for CR, PR, and "CRu" patients)

	day 1	2	3	4-14	
Dexamethasone (mg)	8	8	8	-	} Repeat q mo for 12 cycles
Interferon (x 10  u/m  )	3	3	3	3	

5.7.3 IFN maintenance schedule for these receiving rituximab adjuvant therapy on delayed anti-CD20 arm:.

The IFN will start 1 month after the final FND course. Usually this will be before 12 months, i.e., before rituximab maintenance for patients on the delayed anti-CD20 arm.

When IFN and rituximab are given in the same month, the schedule will be as follows (see also 5.2.3):

	day 1	2+	3	4-15
rituximab (mg/m  )	375	-	-	-
dexamethasone (mg)	8*	8	8	-
Interferon alfa (x 10  u/m  )	-	3	3	3

\* decadron pre-med is optional but encouraged

+ day 2 if possible, but delay of 1-2 days permitted between rituximab and IFN

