## 9.0 CRITERIA FOR REMOVAL FROM THE STUDY

- 9.1 Minor responses or failures to respond after delivering the first 4 courses of treatment in this protocol will be removed from the study.
- 9.2 Patients who relapse after achieving remission will be considered for ABMT or if not eligible will be treated with the salvage protocol of highest priority.

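### Section 10.3c credits arm 1's rise from 12 to 18 months to delayed rituximab, but that rise has no control for interferon or late response, and the planned 18-month comparison with arm 2 does not supply one

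*Combined protocol and SAP*

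**What the plan says.** Section 10.3c asks whether delayed anti-CD20 given after 12 months "will then raise the molecular response rate at 18 months as compared with 12 months in the same patient". It continues: "We will also compare the molecular response at 18 months with patients randomized to arm #2 (concurrent therapy) at the same timepoint". No test, power or rule for missing 18-month samples is given for this item.

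The treatment sections fix what else happens in that window:

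- Section 5.2.3: arm 1 receives six monthly rituximab doses, starting once the 12-month PCR samples are taken. Interferon will usually have begun 3-4 months earlier.
- Section 5.7.3: "The IFN will start 1 month after the final FND course. Usually this will be before 12 months". Section 5.7.2 gives maintenance to CR, PR and CRu patients, "Repeat q mo for 12 cycles". The treatment plan summary makes each cycle 28 days.
- Section 5.3: arm 2 receives rituximab in courses 1-5 only, so it has none between months 12 and 18. Section 5.7.1 gives interferon after FND with or without rituximab, so arm 2 has it too.
- Section 7.2: blood and marrow PCR every 6 months for the first 3 years, in both arms.
- Section 9.2 deals with relapse, among the criteria for leaving the study: "Patients who relapse after achieving remission will be considered for ABMT or if not eligible will be treated with the salvage protocol of highest priority".

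**The concern.** Item c is worded causally: the delayed antibody raises the response rate. A before-after change in one arm supports that only if nothing else could move PCR status between the two samples. Here at least two other things could: interferon, which the protocol itself regards as active (Section 2.2 on remission duration, Section 2.4 on favourable adjuvant experience), and late clearance after FND.

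A second, smaller gap concerns incomplete pairs. A same-patient comparison needs both samples, and the plan does not say how a patient who relapses or dies between 12 and 18 months is counted. If such patients drop out, likely losses of response leave the comparison and the rise looks larger.

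At stake is the reading of the adjuvant strategy. Section 2.4 justifies arm 1 partly by the prospect of higher molecular remission rates after 12 months, and item c is where that prospect is examined most directly.

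**Working it through.** **1. The plan's own figure.** The size is given in Section 10.3a: "Sixty-four PCR-positive patients would be required in each arm to detect a difference of 25% in the 12-month molecular CR rates". The higher rate enters as an assumption there, "assuming that the higher response rate was 85"%, so the lower rate is 60%. The error rates are in the summary: "This assumes a two-sided alpha level of 0.05 and a power of 0.90".

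n = [1.960·√(2·0.725·0.275) + 1.282·√(0.85·0.15 + 0.60·0.40)]² / 0.25² = (1.238 + 0.777)² / 0.0625 ≈ 65 per arm. The arcsine formula gives 63.8, so 64. Power at 64 is 0.896. The stated 64 reproduces. It belongs to the 12-month comparison; item c has no figure to reproduce.

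**2. Does interferon cover the window?** A start 3-4 months before month 12 is month 8-9. Twelve 28-day cycles are 336 days, or 11.0 months, so maintenance ends at about month 19-20. The usual case covers months 12-18. There are exceptions. Interferon is for CR, PR and CRu patients. If FND stops after 6 courses on schedule, course 6 starts at month 4.6, interferon starts at about 5.6 and ends at about 16.6.

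**3. Within-arm rise with no rituximab effect.** At 60% of 64, about 38 patients respond at 12 months and 26 do not. Let c be the fraction of non-responders who convert by 18 months without rituximab, and l the fraction of responders who lose response. Neither is in the documents, so both are assumed.

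Rise = (26c − 38l)/64. The chance of a significant rise is from the exact McNemar test, two-sided 0.05; the nominal chance in that direction is at most 2.5%.

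| c | l | Rise (points) | Chance of a significant rise |
|---|---|---|---|
| 10% | 2% | 2.9 | 2% |
| 10% | 5% | 1.1 | 1% |
| 20% | 2% | 6.9 | 25% |
| 20% | 5% | 5.2 | 10% |
| 20% | 10% | 2.2 | 2% |
| 30% | 2% | 11.0 | 62% |
| 30% | 5% | 9.2 | 35% |
| 30% | 10% | 6.3 | 11% |

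**4. Does the planned 18-month comparison with arm 2 isolate the effect?** Apply c = 20% and l = 5% to both arms, with no rituximab effect after month 12:

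- Arm 1: 0.60 + 0.40·0.20 − 0.60·0.05 = 65%.
- Arm 2: 0.85 + 0.15·0.20 − 0.85·0.05 = 84%.

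The 18-month gap of 19 points mostly carries forward the planned 12-month gap of 25. It shows whether arm 1 has caught up, not what was added after month 12.

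**5. Would the difference between arms in change do better?** With the same c and l in both arms, the expected difference is (0.40 − 0.15)c + (0.85 − 0.60)l = 0.25(c + l). At c = 20% it is 5.5 points for l = 2% and 6.25 points for l = 5%, with no rituximab effect. In simulation (64 per arm, 5% loss, c from 10% to 40%) a z test on this difference gave a false positive in 12% to 41% of trials. It is no replacement.

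**6. Conversion given 12-month status.** Non-responders at 12 months number about 0.40·64 ≈ 26 in arm 1 and 0.15·64 ≈ 10 in arm 2. Fisher's exact test at two-sided 0.05 rejects in 2.4% of trials when both arms convert at 20%. Its power is 25% for 50% vs 20% and 46% for 60% vs 20%. It holds its level but is imprecise.

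**7. Scale of clinical failure in the window.** Section 10.3e gives a typical 3-year FFS of 50% and assumes it exponential. Of patients failure-free at 12 months, 1 − exp(−6·ln 2/36) = 10.9% would fail by month 18. This is a clinical failure rate, not a rate of missing PCR pairs.

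**The case against.** The strongest reply is that item c does not rest on arm 1 alone: its second sentence plans a randomised comparison with arm 2 at 18 months. Items 10.3d and 10.3e add sustained molecular response at 2 years and FFS. A reader might infer that the before-after rise is the only test of the adjuvant strategy. The documents do not support that. What stands is narrower: none of these comparisons uses arm 2's course between 12 and 18 months to separate rituximab from the rest of the treatment.

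A reader might also take arm 2 for a ready control whose change can simply be subtracted. Step 5 shows why not: the arms are planned to start from different rates. Arm 2's roughly 10 non-responders have, moreover, already failed FND plus rituximab.

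Nor do the documents show that the rate would rise on interferon alone. At 10% conversion the chance of a false significant rise is within the nominal 2.5%, and loss of response works against a rise.

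Finally, Section 9.2 might be read as ending PCR at relapse. It does not say so, and Section 7.2 schedules PCR without reference to relapse. What is missing is a counting rule; a systematic loss of samples is not shown.

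**Conclusion.** The concern holds in limited form. Arm 1's rise from 12 to 18 months cannot be assigned to rituximab, because responding patients are usually on interferon over the same months and the comparison has no control. The planned 18-month comparison with arm 2 answers a different question.

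The direction of the error is clear: conversion that would have happened anyway is credited to the antibody. Its size is not. The 1% to 62% range rests wholly on assumed conversion of 10-30% and loss of 2-5%, together with the plan's 60% at 12 months in 64 patients; higher loss lowers it. This is a secondary question, and the 12-month primary comparison is untouched. It should be corrected in the analysis text, without any change to treatment or sampling.

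**What to change.** In Section 10.3c:

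1. State that arm 1's rise from 12 to 18 months is descriptive and will not be attributed to rituximab alone.
2. Report, for arm 1 and arm 2 with confidence intervals, conversion by 18 months among 12-month non-responders and loss of response among 12-month responders. Keep the 18-month comparison between arms, described as a test of catch-up.
3. Count relapse or death between 12 and 18 months as non-response at 18 months, so that these patients stay in the pairs.
4. Do not use the raw difference between arms in change as the test.

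The cost is wording: Section 7.2 already schedules the 12- and 18-month samples in both arms. The price is low precision, which the text should acknowledge, together with the fact that arm 2's non-responders have already had the antibody and are an imperfect control.
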